#### 4.1.2.2 Key Secondary Endpoints for Comparisons to Apremilast

The key secondary endpoints for BMS-986165 compared to apremilast at Week 16 are defined as:

- sPGA 0/1 response assessed as a proportion of subjects with an sPGA score of 0 or 1 with at least a 2-point improvement from baseline
- PASI 75 response assessed as a proportion of subjects who achieve a 75% improvement from baseline in the PASI score
- PASI 90 response assessed as a proportion of subjects who achieve a 90% improvement from baseline in the PASI score
- Change from baseline in PSSD symptom score
- ss-PGA 0/1 assessed as a proportion of subjects with a ss-PGA score of 0 or 1 with at least a 2-point improvement from baseline among subjects with a baseline ss-PGA score  $\geq 3$
- sPGA 0 response assessed as a proportion of subjects with an sPGA score of 0
- PSSD symptom score of 0 assessed as a proportion of subjects with a PSSD symptom score of 0 among subjects with a baseline PSSD symptom score  $\geq 1$

Sponsor: Bristol-Myers Squibb

Protocol no: IM011046

[figure not shown]
The key secondary endpoints for BMS-986165 compared to apremilast at Week 24 are defined as:

- sPGA 0/1 response assessed as a proportion of subjects with an sPGA score of 0 or 1 with at least a 2-point improvement from baseline at Week 24
- PASI 75 response assessed as a proportion of subjects who achieve a 75% improvement from baseline in the PASI score at Week 24
- PASI 90 response assessed as a proportion of subjects who achieve a 90% improvement from baseline in the PASI score at Week 24

[figure not shown]
The key secondary endpoints for BMS-986165 compared to apremilast through Week 52 are defined as:

- sPGA 0/1 response assessed as a proportion of subjects with an sPGA score of 0 or 1 with at least a 2-point improvement from baseline at Week 52 and at Week 24
- PASI 75 response assessed as a proportion of subjects who achieve a 75% improvement from baseline in the PASI score at Week 52 and at Week 24
- PASI 90 response assessed as a proportion of subjects who achieve a 90% improvement from baseline in the PASI score at Week 52 and at Week 24

Sponsor: Bristol-Myers Squibb  
Protocol no: IM011046

Sponsor: Bristol-Myers Squibb  
Protocol no: IM011046

Sponsor: Bristol-Myers Squibb

Protocol no: IM011046

## 4.2 Safety

The safety outcomes include the following:

- Adverse events (AEs)
  - Treatment-emergent adverse events (TEAEs) – defined as:
    - AEs which occur after the first dose of study treatment through 30 days after the final dose of the study treatment or subject's participation in the study if the last scheduled visit occurs at a later time.
  - Treatment-emergent adverse events of interest (AEIs) for the following events:
    - Skin-related AEs
    - Infection AEs, including influenza
    - Creatine kinase (CK) elevation (evaluated as lab toxicity grade 2 or higher)
    - Malignancy
  - SAEs
  - Deaths
- Clinical laboratory parameters
  - Absolute and change from baseline values
  - Laboratory abnormalities (as determined by Controlled Terminology Criteria for Adverse Events [CTCAE v5.0] grading) presented as the worst postbaseline toxicity group
  - Shifts from baseline to maximum postbaseline value
  - Potential drug induced liver injury (DILI) is defined as a subject who meets the following criteria:
    - 1) ALT or AST elevation >3 times ULN  
AND  
▪ 2) Total bilirubin >2 times ULN, without initial findings of cholestasis (elevated serum alkaline phosphatase)  
AND  
▪ 3) No other immediately apparent possible causes of liver function test elevation and hyperbilirubinemia, including, but not limited to, viral hepatitis, preexisting chronic or acute liver disease, or the administration of other drug(s) known to be hepatotoxic.
    - ALT or AST elevation >5 times ULN
- Vital signs
  - Absolute and change from baseline values
  - Marked abnormalities defined by the below categories:
    - Heart rate:
      - Value > 100 and change from baseline > 30
      - Value < 55 and change from baseline < -15
    - Systolic blood pressure:
      - Value > 140 and change from baseline > 20

Sponsor: Bristol-Myers Squibb

Protocol no: IM011046

- Value < 90 and change from baseline < -20
- Diastolic blood pressure:
  - Value > 90 and change from baseline > 10
  - Value < 55 and change from baseline < -10
- Electrocardiograms (ECGs)
  - Absolute and change from baseline values
  - Marked abnormalities defined by the below categories:
    - QT interval corrected using Fridericia's formula (QTcF):
      - 450 -< 480 msec
      - 480 -< 500 msec
      - $\geq$  500 msec
      - $30 < \text{change from baseline} \leq 60$  msec
      - Change from baseline > 60 msec
      - Males: < 450 msec,  $\geq$  450 msec
      - Females: < 470 msec,  $\geq$  470 msec
    - PR interval  $\geq$  200 msec
    - QRS interval  $\geq$  200 msec

In cases where the QT interval is corrected using Bazett's (QTcB) formula is captured instead of QTcF, then QTcB will be converted to QTcF for analyses.

- Eight-Item Patient Health Questionnaire (PHQ-8) total score
  - Absolute and change from baseline values
  - Shifts from baseline scores
- Electronic Columbia-Suicide Severity Rating Scale (eC-SSRS)
  - Suicidal ideation and suicidal behavior responses by visit
  - Shifts from baseline to postbaseline value for suicidal ideation and suicidal behavior
  - Worst postbaseline value for suicidal ideation and behavior

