#### **4.1.6.3 CV Adjudication Committee**

An independent cardiovascular (CV) Adjudication Committee, composed of individuals with relevant expertise, will blindly review and adjudicate cardiovascular and cerebrovascular AEs such as, but not limited to, Major Adverse Cardiovascular Events (MACE) that include death, non-fatal myocardial infarction, non-fatal stroke; revascularization procedures; heart failure; dysrhythmias; heart blocks; and thrombotic events reported in the study per criteria specified in a separate charter. Additional information about cardiovascular and cerebrovascular AEs may be collected on the case report form in order to characterize and understand them. The Adjudication Committee members will be blinded to the treatment assignment of subjects. The structure, responsibilities, and procedures of the Adjudication Committee will be outlined in a charter. The Adjudication Committee is distinct from the DMC and Adjudication Committee members will not be investigators on the study.

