#### **9.5.2      *Vital Signs and ECGs***

Vital signs and ECGs will be summarized as raw, change from baseline, and change from maximum postbaseline value. Incidence of abnormal ECG findings will also be summarized.

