## 6.2.5 ECGs

ECG parameters will be summarized by time point, as applicable. The following summaries will be provided for each parameter:

- Absolute and change from baseline values
- Number and percentage of subjects for the following:
  - Marked abnormality for each abnormality category as defined in Section 4.2

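### The only numeric QRS category in the SAP is set at 200 msec, the same figure as PR and without a reason, so it would probably stay empty and miss individual QRS widening below that level

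*SAP*

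**What the plan says.** SAP 4.2 (Safety) lists the ECG marked abnormalities. QTcF has three graded bands (from 450, from 480 and from 500 msec), two change-from-baseline bands, the upper one being "Change from baseline > 60 msec", and separate limits for men (450 msec) and women (470 msec). The list ends with one line each for the other two intervals: "PR interval $\geq$ 200 msec" and "QRS interval $\geq$ 200 msec".

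SAP 6.2.5 takes its ECG subject counts from that list: "Marked abnormality for each abnormality category as defined in Section 4.2". It also says that "ECG parameters will be summarized by time point, as applicable", with absolute and change-from-baseline values for each parameter.

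Protocol 9.5.2 is broader. "Vital signs and ECGs will be summarized as raw, change from baseline, and change from maximum postbaseline value", and "Incidence of abnormal ECG findings will also be summarized". Protocol 4.1.6.3 sends cardiovascular adverse events to blinded adjudication, including "heart failure; dysrhythmias; heart blocks; and thrombotic events reported in the study".

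Neither document gives a QRS reference range, an expected QRS distribution or a reason for using one figure for both PR and QRS.

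**The concern.** PR and QRS are different intervals, so one shared limit with no explanation needs checking. It matters more for QRS because the rest of the list is better graded. QTcF has several levels and change bands, and each vital-sign category in SAP 4.2 combines a value with a change from baseline. QRS has one fixed cut-off and nothing beneath it.

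If the cut-off lies far above the values these subjects will have, the row will show zero in every arm whatever the drug does short of that level. A reader of the study report could take the zeros as reassurance about ventricular conduction when they reflect only the cut-off. The trial adjudicates dysrhythmias and heart blocks, so conduction is a safety question that it means to address.

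**Working it through.** **Inputs from the documents.** QRS limit 200 msec and PR limit 200 msec (SAP 4.2). About 600 subjects randomized 2:1:1, that is about 300, 150 and 150 (protocol synopsis and 4.2). ECGs after baseline at Weeks 16, 24 and 52 (protocol Tables 2 and 3). The 200 msec limit is a fixed cut-off, so the plan has no calculated figure to reproduce.

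**Assumption, not in the documents.** QRS roughly normal with mean m of 90 to 110 msec and SD s of 10 to 25 msec.

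**Step 1: expected count at one reading.** p = P(Z ≥ (200 − m)/s), expected count = 600p, and P(at least one) = 1 − (1 − p)^600.

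| m (msec) | s (msec) | (200 − m)/s | p | Expected in 600 | P(at least one) |
|---|---|---|---|---|---|
| 90 | 10 | 11.0 | about 0 | 0.00 | 0.00 |
| 100 | 15 | 6.7 | 1.3 × 10⁻¹¹ | 0.00 | 0.00 |
| 100 | 25 | 4.0 | 3.2 × 10⁻⁵ | 0.02 | 0.02 |
| 110 | 25 | 3.6 | 1.6 × 10⁻⁴ | 0.10 | 0.09 |

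In the 300-subject arm the largest expected count is 0.05. Over the three scheduled post-baseline ECGs, the expected number of subjects ever reaching the limit in the least favourable row is at most 3 × 0.0955 = 0.29.

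**Step 2: without the normal tail.** A normal curve may describe rare wide-QRS subjects poorly. Assume instead that a fixed share of subjects is at or above 200 msec. A share of 0.01% gives 0.06 expected in 600 (P(at least one) 0.06), 0.1% gives 0.6 (0.45), and 1% gives 6 (0.998). Several counts therefore need a share near 1%, which nothing in the documents supports. The category also has no baseline condition, so subjects already that wide at entry would be counted as if they were new.

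**Step 3: what the continuous summary can show.** For 300 versus 150 subjects, SE = SD × √(1/300 + 1/150) = 0.1 × SD, and power ≈ Φ(difference/SE − 1.96). The SD of change is assumed. The SAP plans no ECG test, so this only gauges sensitivity.
- SD 10 msec, SE 1: a 3 msec shift gives Φ(1.04) = 0.85, and 5 msec gives more than 0.99.
- SD 20 msec, SE 2: a 3 msec shift gives Φ(−0.46) = 0.32, and 5 msec gives Φ(0.54) = 0.70.

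A few outliers behave differently. If 3 of 300 subjects widened by 40 msec, the arm mean would move by 3 × 40/300 = 0.4 msec, well under one SE in either case.

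**Step 4: background at a lower limit.** At 120 msec, with mean 90 and SD 10, z = 3.0 and 600 × 0.00135 ≈ 1 subject. With mean 100 and SD 15, z = 1.33 and 600 × 0.091 ≈ 55. At the widest assumption of Step 1 (mean 110, SD 25), z = 0.4 and 600 × 0.345 ≈ 207. These are single-reading counts with no drug effect, before any baseline restriction.

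**The case against.** A reader might infer that the trial cannot detect conduction slowing. The documents do not support that. SAP 6.2.5 keeps absolute and change-from-baseline values for each ECG parameter, and Step 3 shows that these could reveal a general shift. Protocol 9.5.2 also plans the incidence of abnormal ECG findings. Clinically significant ECG results become adverse events under protocol Appendix 3, and heart blocks go to blinded adjudication. None of these uses the 200 msec limit, and a QRS that reached 200 msec would itself be counted.

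These routes have limits. SAP 6.2.5 does not repeat the protocol's abnormal-ECG incidence, although SAP 2.5 does not list it as dropped and the SAP is to be read with the protocol. Adjudication covers reported adverse events, and ECGs are read by the investigator or a designee (protocol 8.4.3), so asymptomatic widening need not reach the committee.

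A reader might also infer that the QRS figure was copied from the PR line. That is plausible but unproven. The list is of marked abnormalities, not normal limits, and QTcF also has a band from 500 msec, so a high cut-off is not in itself inconsistent. PR has no change band either.

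Finally, a near-empty row is a consequence of assumed values, not something the documents show. That stands, and the conclusion is worded accordingly.

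**Conclusion.** The point holds as a limited defect in one descriptive safety category. The documents themselves establish that PR and QRS share 200 msec without a reason, that QRS has no other numeric category, and that SAP 6.2.5 draws its ECG subject counts from this list. Under the assumed mean of 90 to 110 msec and SD of 10 to 25 msec, about 0 to 0.1 of 600 subjects would reach the limit at one reading. The row would then probably be zero in every arm and could not flag individual widening that stays below 200 msec.

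The remaining ECG and adverse-event outputs mean that the plan as a whole is not blind to conduction effects. They are weak for a few subjects with silent widening, which is what a categorical count is for. No efficacy endpoint, error control or analysis population is affected. The correction is worth making because it is cheap and makes the row informative.

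**What to change.** Before database lock, replace the 200 msec QRS figure in SAP 4.2 with the QRS-specific limit from the sponsor's own ECG standard. That limit is assumed here to lie near 110 to 120 msec; the documents do not supply it. Define the count as subjects at or above the limit after baseline who were below it at baseline. Leave the PR line unchanged. SAP 1.0 already provides for an updated version to be approved before final database lock.

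The cost is one figure, one definition and a rerun of one descriptive table. The table will also show some background. With a mean of 90 to 100 msec and an SD of 10 to 15 msec, about 1 to 55 of 600 subjects would be at or above 120 msec at a single reading without any drug effect. Wider assumptions give more, and the baseline restriction gives fewer. The row must therefore be read against placebo through Week 16 and against apremilast, not as a count on its own.

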## 5.0 Populations for Analyses

The following analysis sets will be used in the summary and analysis of study data:

- **Enrolled population:** All subjects who sign informed consent.
- **Full Analysis Set (FAS):** All subjects who are randomized. Following the intent-to-treat (ITT) principle, subjects will be analyzed according to the treatment group assigned at randomization. The FAS will be the primary efficacy analysis population.
- **Per Protocol Set (PPS):** A subset of the FAS who are compliant with study treatment and who do not have any relevant protocol deviations that may impact the coprimary efficacy endpoint assessments. The PPS will be analyzed according to the treatment assigned at randomization. The PPS will be a supportive efficacy analysis population and only the co-primary endpoints will be analyzed using this set.
- **As-treated population:** All randomized subjects who take at least one dose of study treatment. Subjects will be analyzed according to treatment received.

## 6.0 Statistical Analyses

Descriptive summaries and analyses will be presented for data captured throughout the study using the following treatment groups.

During the first 16 weeks of treatment, summaries will be provided for the following treatment groups:

- BMS-986165 6 mg QD
- Apremilast
- Placebo

During the first 24 weeks of treatment, summaries will be provided for the following treatment groups:

- BMS-986165 6 mg QD (subjects continuously taking BMS-986165 6 mg QD)
- Apremilast

Summaries will be provided for subjects who have continuous treatment throughout the entire study with either BMS-986165 or apremilast using the following treatment groups:

- BMS-986165 6 mg QD
- Apremilast

Summaries of all subjects exposed to BMS-986165 6 mg QD will also be provided as applicable. Adverse events will be summarized using exposure-adjusted incidence rates (EAIR) for these summaries.

Please note that there will be no Chinese subjects in the apremilast group due to lack of market approval of the agent in China.

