### Week 24 activities

[figure not shown]
At Week 24, subjects originally randomized to apremilast who do not achieve PASI 50 response will be switched in a blinded manner to BMS-986165 6 mg QD. Subjects in the apremilast treatment arm who achieve PASI 50 response at Week 24 will continue to receive apremilast in a blinded manner through Week 52.

During the Week 24 assessment, a subject who has an sPGA  $\geq 3$  or ss-PGA $\geq 3$  may be treated with restricted topicals/shampoos as described in the protocol (Section 6.7.1). These treatments may only be initiated at Week 24, and not at subsequent time points. A subject who is provided these treatments at Week 24 may use them as needed per the investigator's judgement through Week 52.

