### 6.1 Efficacy Analyses

All efficacy analyses will be performed using the FAS, unless otherwise specified.

Tests of significance of BMS-986165 6 mg QD vs. placebo for the coprimary endpoints will be two-sided with a significance level of 0.05. Both coprimary endpoints need to demonstrate statistical significance to result in a successful study.

The key secondary endpoints will be tested with a two-sided significance level of 0.025 to compare BMS-986165 6mg QD vs. placebo and vs. apremilast. A hierarchical testing approach will be used for testing of

Sponsor: Bristol-Myers Squibb

Protocol no: IM011046

key secondary endpoints (see [Section 6.1.3](#)). Two-sided 95% confidence intervals (CIs) will be provided for all efficacy estimates. [REDACTED]

Coprimary and key secondary efficacy endpoints will be displayed graphically by treatment group and visit, as applicable. All efficacy endpoints will be summarized descriptively.

Due to small sample sizes in China and Japan and differences in stratification factors, analyses will be stratified by a combination of the stratification factors used in randomization. The stratified levels are provided below:

- US/PRIOR USE/< 90 KG
- US/PRIOR USE/≥90 KG
- US/NAÏVE/<90 KG
- US/NAÏVE/≥90 KG
- ROW/PRIOR USE/< 90 KG
- ROW/PRIOR USE/≥90 KG
- ROW/NAÏVE/<90 KG
- ROW/NAÏVE/≥90 KG
- JAPAN/PRIOR USE
- JAPAN/NAÏVE
- CHINA/PRIOR USE
- CHINA/NAÏVE

If there is not at least one subject per treatment group in each of the China and Japan strata, then these regions will be collapsed together to form the following stratified levels for analyses:

- US/PRIOR USE/< 90 KG
- US/PRIOR USE/≥90 KG
- US/NAÏVE/<90 KG
- US/NAÏVE/≥90 KG
- ROW/PRIOR USE/< 90 KG
- ROW/PRIOR USE/≥90 KG
- ROW/NAÏVE/<90 KG
- ROW/NAÏVE/≥90 KG
- ASIA/PRIOR USE
- ASIA/NAÏVE

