#### Imputation Methodology for Week 52 Endpoints (for comparison of BMS-986165 6 mg QD to apremilast)

The key secondary endpoints included in this analysis are the following:

- sPGA 0/1 response with at least a 2-point improvement from baseline at Week 52 and at Week 24

Sponsor: Bristol-Myers Squibb

Protocol no: IM011046

- PASI 75 response at Week 52 and at Week 24
- PASI 90 response at Week 52 and at Week 24

Subjects must meet response criteria at both Weeks 24 and 52 in order to be considered a responder. Those who do not meet response criteria at both weeks will be considered a nonresponder. NRI will be used for the above key secondary endpoints for subjects who:

- Discontinue treatment or study prior to Week 52
- Have missing Week 52 or Week 24 endpoint data
- Switch from apremilast to BMS-986165 at Week 24 for Week 24 PASI 50 nonresponders

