## 6.2 Safety

Summaries of safety data will be presented by period and treatment group, as applicable, for the As-treated population.

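### The SAP's only listed 52-week BMS-986165 versus apremilast columns leave out apremilast subjects switched at Week 24, so they are not a randomised comparison

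*SAP*

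**What the plan says.** SAP 6.0 lists four sets of columns: Weeks 0–16 (three arms), Weeks 0–24 (BMS-986165 and apremilast), the full study, and everyone exposed to BMS-986165.

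- **Full-study set:** "Summaries will be provided for subjects who have continuous treatment throughout the entire study with either BMS-986165 or apremilast", with one column per drug. The SAP does not define continuous treatment.
- **All-exposed set:** "Summaries of all subjects exposed to BMS-986165 6 mg QD will also be provided as applicable". AEs in this set are given as EAIR. No matching set is listed for apremilast.
- **Week 24 switch (SAP 2.1):** "subjects originally randomized to apremilast who do not achieve PASI 50 response will be switched in a blinded manner to BMS-986165 6 mg QD". There is no corresponding exit for BMS-986165 nonresponders.
- **COVID-19 (SAP 6.6.1 and 6.6.2):** some subjects may be moved to BMS-986165 from another treatment between Weeks 24 and 52. No safety analysis is modified for this.
- **Safety population (SAP 6.2):** "Summaries of safety data will be presented by period and treatment group, as applicable, for the As-treated population".
- **Protocol 9.4 and 9.5:** after Week 16 both list a plain apremilast column with no continuous-treatment condition. SAP 2.5, which lists the important changes from the protocol, does not mention the new restriction.

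**The concern.** Membership of the full-study columns depends on what happens after randomisation, and one route out is open to the apremilast arm only. A subject who fails PASI 50 on apremilast at Week 24 is no longer continuously on apremilast. A subject who fails it on BMS-986165 carries on and is counted. The COVID-19 switch works in the same direction, because placebo subjects have all moved to BMS-986165 by Week 16 and only apremilast subjects are left to be moved.

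At stake is the comparator's 52-week AE profile. It would be read from a group selected on response, beside a BMS-986165 column without that selection. AEs that switched subjects had on apremilast before Week 24 would be absent from the only listed 52-week display with an apremilast column.

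**Working it through.** The documents give no figure to reproduce: no switch rate, dropout rate or AE rate is stated. The only arithmetic they support is arm size: 600 subjects at 2:1:1 give nominally 300 BMS-986165, 150 placebo and 150 apremilast.

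**Step 1. Who is removed under each reading.**

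| Subject | Never-switched reading | Completer reading |
|---|---|---|
| Apremilast, switched at Week 24 or for COVID-19 | out | out |
| BMS-986165, PASI 50 nonresponder, still on drug | in | in |
| Discontinuer, either arm | in | out |

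The first two rows do not depend on how the term is read. The third does. On the completer reading, discontinuations for AEs would be zero in this set by construction.

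**Step 2. Effect on an AE rate (assumed inputs).** Let s be the share of the apremilast arm removed and r the AE rate in those removed divided by the rate in those kept, with equal exposure per subject. Then full-arm rate / column rate = (1 − s) + s·r, and understatement = 1 − 1/[(1 − s) + s·r].

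- s = 20%, r = 1.2: 0.80 + 0.24 = 1.04; 1 − 1/1.04 = 3.8%
- s = 35%, r = 1.5: 0.65 + 0.525 = 1.175; 1 − 1/1.175 = 15%
- s = 40%, r = 2.0: 0.60 + 0.80 = 1.40; 1 − 1/1.40 = 28.6%
- r = 1: no effect for any s
- r below 1: the sign reverses; for example s = 40%, r = 0.8 gives 0.60 + 0.32 = 0.92, and 1/0.92 − 1 = 8.7% overstatement

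This concerns the apremilast column alone. On the completer reading the BMS-986165 column is also selected, so the contrast between columns could move by less.

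**Step 3. Effect on descriptive response (assumed inputs).** Those removed count as nonresponders under nonresponder imputation (NRI), so column rate = NRI rate / retained share. Let d be the share discontinued and f the apremilast share switched. The retained share is 1 and (1 − f) if only switchers go. It is (1 − d) and (1 − d − f) if discontinuers go too. Assume NRI response of 50% on BMS-986165 and 25% on apremilast, a 25-point difference. Each cell gives BMS-986165 versus apremilast; differences use unrounded rates.

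| d (BMS-986165 / apremilast) | f | Switchers out only | Switchers and discontinuers out |
|---|---|---|---|
| 10% / 10% | 20% | 50% vs 31.25%; 18.75 points (n 300 vs 120) | 55.6% vs 35.7%; 19.8 points (n 270 vs 105) |
| 15% / 20% | 30% | 50% vs 35.7%; 14.3 points (n 300 vs 105) | 58.8% vs 50.0%; 8.8 points (n 255 vs 75) |
| 15% / 20% | 40% | 50% vs 41.7%; 8.3 points (n 300 vs 90) | 58.8% vs 62.5%; −3.7 points (n 255 vs 60) |

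In every row the selection lifts the apremilast column more, so the apparent BMS-986165 advantage shrinks.

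**The case against.** The case on the other side is substantial, and it rules out four stronger conclusions that a reader might draw.

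- **That discontinuers are dropped.** This is only one reading. The 24-week set labels its first column "BMS-986165 6 mg QD (subjects continuously taking BMS-986165 6 mg QD"), apparently to separate it from placebo subjects who switched, which points to never switched. TEAEs leading to discontinuation have their own tables (SAP 6.2.1.3), and the EAIR definition (SAP 8.1) gives event-free discontinuers exposure plus 30 days. These fit the never-switched reading better.
- **That the Week 52 efficacy comparison is biased by this set.** It is not. SAP 6.1 says: "All efficacy analyses will be performed using the FAS, unless otherwise specified". For the Week 52 key secondary endpoints (SAP 6.1.2.1), NRI applies to subjects who "Discontinue treatment or study prior to Week 52" and to those switched at Week 24. The COVID-19 exclusion in SAP 6.6.1 is a separate matter.
- **That the set favours the sponsor's drug.** For response the larger lift goes to apremilast. For AEs, if those removed have the higher rate, apremilast again looks better.
- **That no 52-week output keeps all apremilast experience.** Total apremilast duration is displayed, including time before a switch or early stop (SAP 6.3.4.1). Discontinuation at any time, with reason, uses the Full Analysis Set (FAS) as denominator (SAP 6.3.1).

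It can also be said that EAIR is defined per treatment received (SAP 8.1) and listed for TEAEs without limitation to BMS-986165 (SAP 6.2.1). Parts of the SAP are redacted, and it refers to a data presentation plan that is not available here, so a suitable table may exist. That limits the claim to the column sets listed. Within those, the general EAIR definition assigns no 52-week apremilast column that brings the switched subjects back, and SAP 6.0 ties the all-exposed EAIR summary to BMS-986165.

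**Conclusion.** The point holds for the 52-week descriptive columns. On either reading of the undefined term, the apremilast column excludes subjects switched at Week 24 for PASI 50 nonresponse, and any switched because of COVID-19, together with their pre-switch events. BMS-986165 nonresponders remain. Differences between the two columns cannot be read as treatment differences.

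The size cannot be established from the documents. The 4–29% understatement of the apremilast AE rate assumes 20–40% removed and a rate ratio of 1.2–2.0. Nothing in the plan shows that PASI 50 nonresponders have more AEs, so zero or a reversal is possible.

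The Week 52 key secondary tests, disposition on the FAS, and the 16- and 24-week summaries, which retain apremilast events before the switch, are not touched. This is a weakness in descriptive reporting that merits a change. It does not threaten the primary or key secondary conclusions.

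**What to change.** 1. Define the 52-week safety columns as all As-treated subjects by initial treatment, BMS-986165 and apremilast. Count events and exposure up to switch or discontinuation, with the existing 30-day rule where it applies, and report EAIR for both. The two event-free branches in SAP 8.1 do not name a subject who switches, so state how apremilast time is closed for them.
2. Define continuous treatment, and say whether discontinuers contribute.
3. Keep the present table only as a supplement labelled as a selected, non-randomised subset.
4. Record the change from the protocol's post-Week 16 apremilast column in SAP 2.5.

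The cost is SAP wording and one set of tables. SAP 6.3.4.1 already derives apremilast duration to the switch or early stop, and SAP 8.1 already defines EAIR by treatment, so no new data are needed.
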